## Infusion-Related Reactions

Severity Grade of the Event (NCI CTCAE version 4.03)	Dose Modifications	Toxicity Management
Any Grade	General Guidance	For Any Grade: 

– Manage per institutional standard at the discretion of investigator.

– Monitor patients for signs and symptoms of infusion-related reactions (e.g., fever and/or shaking chills, flushing and/or itching, alterations in heart rate and blood pressure, dyspnea or chest discomfort, or skin rashes) and anaphylaxis (e.g., generalized urticaria, angioedema, wheezing, hypotension, or tachycardia).

Grade 1 or 2	For Grade 1: 
The infusion rate of study drug/study regimen may be decreased by 50% or temporarily interrupted until resolution of the event.
 For Grade 2: 
The infusion rate of study drug/study regimen may be decreased 50% or temporarily interrupted until resolution of the event.
 
Subsequent infusions may be given at 50% of the initial infusion rate.
	For Grade 1 or 2: 

– Acetaminophen and/or antihistamines may be administered per institutional standard at the discretion of the investigator.

– Consider premedication per institutional standard prior to subsequent doses.

– Steroids should not be used for routine premedication of Grade <math>\leq 2</math> infusion reactions.

Grade 3 or 4	For Grade 3 or 4: 
Permanently discontinue study drug/study regimen.
	For Grade 3 or 4: 

– Manage severe infusion-related reactions per institutional standards (e.g., IM epinephrine, followed by IV diphenhydramine and ranitidine, and IV glucocorticoid).

CTCAE Common Terminology Criteria for Adverse Events; IM intramuscular; IV intravenous; NCI National Cancer Institute.

Clinical Study Protocol  
Drug Substance Tremelimumab  
Study Number **ESR-14-10744**  
Edition Number 8  
Date 17 April 2019

## Non-Immune-Mediated Reactions

Severity Grade of the Event (NCI CTCAE version 4.03)	Dose Modifications	Toxicity Management
Any Grade	Note: Dose modifications are not required for AEs not deemed to be related to study treatment (i.e., events due to underlying disease) or for laboratory abnormalities not deemed to be clinically significant.	Treat accordingly, as per institutional standard.
Grade 1	No dose modifications.	Treat accordingly, as per institutional standard.
Grade 2	Hold study drug/study regimen until resolution to $\leq$ Grade 1 or baseline.	Treat accordingly, as per institutional standard.
Grade 3	Hold study drug/study regimen until resolution to $\leq$ Grade 1 or baseline. For AEs that downgrade to $\leq$ Grade 2 within 7 days or resolve to $\leq$ Grade 1 or baseline within 14 days, resume study drug/study regimen administration. Otherwise, discontinue study drug/study regimen.	Treat accordingly, as per institutional standard.
Grade 4	Discontinue study drug/study regimen (Note: For Grade 4 labs, decision to discontinue should be based on accompanying clinical signs/symptoms, the Investigator's clinical judgment, and consultation with the Sponsor.).	Treat accordingly, as per institutional standard.

Note: As applicable, for early phase studies, the following sentence may be added: "Any event greater than or equal to Grade 2, please discuss with Study Physician."

AE Adverse event; CTCAE Common Terminology Criteria for Adverse Events; NCI National Cancer Institute.

## **6. RESTRICTIONS DURING THE STUDY AND CONCOMITANT TREATMENT(S)**

### **6.1 Restrictions during the study**

#### **Contraception**

Female subjects of childbearing potential who are sexually active with a non-sterilized male partner must use at least one highly effective method of contraception (Table 5) from the time of screening and must agree to continue using such precautions for 90 days after the last dose of mono-therapy MEDI4736 or for 180 days after last dose of combination therapy with MEDI4736 and tremelimumab. The male partner of a female subject must also use male condom plus spermicide throughout this period. Cessation of birth control after this point should be discussed with a responsible physician. Not engaging in sexual activity is an acceptable practice; however, occasional abstinence, the rhythm method, and the withdrawal method are not acceptable methods of contraception. Female patients should refrain from breastfeeding and egg cell donation throughout this period.

- Females of childbearing potential are defined as those who are not surgically sterile (i.e., bilateral tubal ligation, bilateral oophorectomy, or complete hysterectomy) or postmenopausal (defined as 12 months with no menses without an alternative medical cause).
- Effective methods (including highly effective methods) of contraception are described in Table 5. A highly effective method of contraception is defined as one that results in a low failure rate (ie, less than 1% per year) when used consistently and correctly. Note that not all methods in Table 1 are considered highly effective.
- Non-sterilized male subjects who are sexually active with a female partner of childbearing potential must use male condom plus spermicide (see Table 5) from screening through 90 days after the last dose of mono-therapy MEDI4736 or for 180 days after last dose of combination therapy with MEDI4736 and tremelimumab. Not engaging in sexual activity is an acceptable practice; however, occasional abstinence, the rhythm method, and the withdrawal method are not acceptable methods of contraception. Male patients should refrain from sperm donation throughout this period. Female partners of a male subject must use an effective method of contraception throughout this period.

**Table 5      Effective Methods of Contraception**

Barrier/Intrauterine Methods	Hormonal Methods

 
Male or female condom with or without spermicidea,b,c
 
Female cap, diaphragm or sponge with spermicidea,b,c
 
Copper T intrauterine devicee
 
Levonorgesterel-releasing intrauterine system (eg, Mirena®)d,e
 
	
 
Implantse
 
Hormone shot or injectione
 
Combined pille
 
Minipillb
 
Patche
 

a Female partners of male subjects must use an effective method of birth control

b Not highly effective (i.e. failure rate of >1% per year)

c A combination of male condom with either cap, diaphragm or sponge with spermicide (double barrier methods) are also considered acceptable, but not highly effective, birth control methods

d This is also considered a hormonal method

e Highly effective (i.e. failure rate of <1% per year)

## Blood donation

Subjects should not donate blood while participating in this study, or for at least 90 days following the last infusion of MEDI4736 or tremelimumab.

## 6.2      Concomitant treatment(s)

### 6.2.1      Permitted concomitant medications

Investigators may prescribe concomitant medications or treatments (e.g., acetaminophen, diphenhydramine) deemed necessary to provide adequate prophylactic or supportive care except for those medications identified as “excluded” as listed in Section 6.2.2.

### 6.2.2      Excluded Concomitant Medications

The following medications are considered exclusionary during the study.

1. Any investigational anticancer therapy other than MEDI4736.
2. Any concurrent chemotherapy, radiotherapy (except palliative radiotherapy), immunotherapy, biologic or hormonal therapy for cancer treatment, other than tremelimumab and surgical resection. Concurrent use of hormones for noncancerous-related conditions (e.g., insulin for diabetes and hormone replacement therapy) is

acceptable. Local treatment of isolated lesions for palliative intent also is acceptable (e.g., by local surgery or radiotherapy).

3. Immunosuppressive medications including, but not limited to systemic corticosteroids at doses not exceeding 10 mg/day of prednisone or equivalent, methotrexate, azathioprine, and TNF- $\alpha$  blockers. Use of immunosuppressive medications for the management of investigational product-related AEs or in subjects with contrast allergies is acceptable. In addition, use of inhaled and intranasal corticosteroids is permitted. A temporary period of steroids will be allowed for different indications, at the discretion of the principal investigator (e.g., chronic obstructive pulmonary disease, radiation, nausea, etc.).
4. Live attenuated vaccines within 30 days of MEDI4736 or tremelimumab dosing (i.e., 30 days prior to the first dose, during treatment with MEDI4736 and for 30 days post discontinuation of MEDI4736). Inactivated viruses, are permitted.

## 7. STUDY PROCEDURES

Subjects with MPM who are eligible for the study will be enrolled. Subjects first will undergo surgical mediastinal lymph node biopsy (cervical mediastinoscopy) and simultaneous surgical biopsy of the pleural tumor by thoracoscopy, at which time tumor tissue (goal of 2 g, which is generally available) and 25 ml of peripheral blood will be collected. These procedures are performed as our standard of care in the treatment of subjects with MPM. Three days to three weeks later subjects will receive either MEDI4736 (15 mg/kg once intravenously) or MEDI4736 (1500 mg once intravenously) + tremelimumab (75 mg once intravenously). Subjects under 30 kg will be treated with weight-based dosing for both MEDI4736 and Tremelimumab combination therapy. These patients are excluded from fixed based dosing to limit endotoxin exposure from the drug preparations. A control group will include patients who are not treated with MEDI4736 or Tremelimumab. One to six weeks after treatment, subjects will undergo resectional surgery including extrapleural pneumonectomy or pleurectomy/decortication at which time the tumor will be removed (typically 200-1000g) and obtained for study. Blood (25ml) also will be obtained for study. In addition, the sixth rib will be extracted at the time of the resectional procedure, as is routinely done during these procedures. After the removal of the tumor, our standard protocol (in the presence of conserved renal function) includes intraoperative heated chemotherapy using a lavage of

Clinical Study Protocol

Drug Substance Tremelimumab

Study Number **ESR-14-10744**

Edition Number 8

Date 17 April 2019

intracavitary cisplatin (Sugarbaker et al, 2013, 2014; Richards et al., 2006). Subjects will be followed for at least 90 days following the administration of the study drug for potential AEs or SAEs related to the study drug. Subjects will be followed for a longer period of time as standard of care.

## **7.1 Schedule of study procedures**

Before study entry, throughout the study, and following study drug discontinuation, various clinical and diagnostic laboratory evaluations are outlined. The purpose of obtaining these detailed measurements is to ensure adequate safety and tolerability assessments. Clinical evaluations and laboratory studies may be repeated more frequently if clinically indicated. The Schedules of Assessments during the screening and treatment period is provided following the Protocol Synopsis.

### **7.1.1 Screening Phase**

Screening procedures will be performed up to 28 days before or on Day 1, unless otherwise specified. All subjects must first read, understand, and sign the IRB/REB/IEC-approved ICF before any study-specific screening procedures are performed. After signing the ICF, completing all screening procedures, and being deemed eligible for entry, subjects will be enrolled in the study. Procedures that are performed prior to the signing of the ICF and are considered standard of care may be used as screening assessments if they fall within the 28-day screening window.

All subjects who screen for this study will have a clinical diagnosis of MPM (based upon CT, and/or PET-CT, and or MRI radiographic findings) but not all subjects will have had this diagnosis confirmed by a tissue biopsy. In either case patients undergo thoracoscopy to assess resectability of disease, and to obtain tissue or additional tissue, when necessary, for diagnosis. Thoracoscopy will be performed in these subjects after signing the ICF.

The following procedures will be performed during the Screening Visit:

- Informed Consent
- Review of eligibility criteria
- Medical history and demographics
- Complete physical exam
- ECOG Performance Status
- Vitals signs, weight and height
- Review of prior/concomitant medications

- Imaging by CT/MRI, if applicable to study
- Clinical laboratory tests for:
  - Hematology (see Table 6)
  - Clinical chemistry (see Table 7)
  - TSH
  - Coagulation (PT, PTT, INR)
  - Creatinine Clearance
  - Serum pregnancy test (for women of childbearing potential only)
  - Hepatitis serologies
  - Urinalysis (see Table 8)
  - Disease-specific tumor markers

### **7.1.2 Treatment Phase**

Procedures to be conducted during the treatment phase of the study are presented in the Schedule of Assessments.

Following the Screening Phase, subjects with MPM who are enrolled in the study will undergo surgical mediastinal lymph node biopsy (cervical mediastinoscopy) to evaluate nodal status and simultaneous surgical biopsy of the pleural tumor by thoracoscopy under general anesthesia, at which time tumor tissue (at least 2 g) and peripheral blood (25ml) will be collected for the study. These procedures are performed as our standard of care in the treatment of these subjects. The thoracoscopy procedure is part of our standard of care in both in subjects who have had a previous tissue biopsy and those who have not had a previous biopsy. It is performed to determine resectability of the tumor and to obtain tissue to confirm tissue diagnosis. In subjects who are consented to the study who have a suspected (clinical) diagnosis of MPM but not a tissue diagnosis, if the thoracoscopy procedure reveals that the subject does not have MPM, then these subjects will be removed from the study and their tissue and blood samples will be destroyed. These subjects will be replaced in the study.

Three days to three weeks later subjects will be treated with either MEDI4736 (15 mg/kg once intravenously) or MEDI4736 (1500 mg once intravenously) + tremelimumab (75 mg once intravenously). Subjects under 30 kg will be treated with weight-based dosing for both MEDI4736 and Tremelimumab combination therapy. These patients are excluded from fixed based dosing to limit endotoxin exposure from the drug preparations. A control group will include patients who are not treated with MEDI4736 or Tremelimumab. One to six weeks after treatment, subjects will undergo resectional surgery including extrapleural pneumonectomy or pleurectomy/decortication under general anesthesia, at which time the

Clinical Study Protocol

Drug Substance Tremelimumab

Study Number **ESR-14-10744**

Edition Number 8

Date 17 April 2019

tumor will be removed (typically 200-1000g) and obtained for study. Blood (25ml) also will be obtained for the study. The sixth rib will be obtained at the time of the resectional procedure as part of the routine procedure. After the removal of the tumor, our standard protocol (in the presence of conserved renal function) includes intraoperative heated chemotherapy using a lavage of intracavitary cisplatin.

### **7.1.3 End of Treatment**

Subjects will be followed for a minimum of 12 months following entry into the study. As per standard of care, the great majority of patients will receive care with our group for the rest of their life, enabling measurement of disease free and overall survival, in our secondary objectives.

In general, subjects will spend approximately 8-14 days in the hospital following resection. After discharge from the hospital, subjects will return for follow-up visits at 1 week, 2 weeks, and 4 weeks and then every 4 months until death. Chest CT scans will be obtained every 4 months starting at the first 4-month visit.

Assessments for subjects who have completed MEDI4736 or MEDI4736 + tremelimumab but did not have resection are provided in APPENDIX B.

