**Schedule of study assessments: Screening and Treatment Period (24 months: maximum of 1 dose)**

Visit	Screening (Up to 28 days before or on Day 1)				Oncology Visit	Infusion (3 days-3 weeks after mediastinoscopy & thoracoscopy)	All assessments to be performed pre-infusion unless stated otherwise		
		Baseline	Mediastinoscopy & Thoracoscopy				Clinic Visit	Surgical Resection 1-6 weeks after infusion i	Follow-up (after expected average 2 week hospital stay)
Day	-28 to 1	1							
Week	-4 to 1	0	0-1	0-3	0-3		1-6	1-6	After discharge from hospital 1 week later, then 2 weeks later, then 4 weeks later. (±7 days)
Weight	X	X					X		
Electrocardiogram d		X			X				X (week 16 only)
Adverse event/serious adverse event assessment	X	X							All visits
Concomitant medications	X	X							All visits
Palliative radiotherapy									As clinically indicated
ECOG performance status	X	X					X		
Liver enzyme panel f						X			
Serum Chemistry (Complete clin chem. panel including Liver Enzymes, Amylase, Lipase) e	X	X					X		
Thyroid function tests (TSH and fT3 and fT4) f	X	X					X		

Clinical Study Protocol

Drug Substance Tremelimumab

Study Number **ESR-14-10744**

Edition Number 8

Date 17 April 2019

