	Grade 2 (AST or ALT $>3.0 \times \text{ULN}$ and $\leq 5.0 \times \text{ULN}$ and/or TB $>1.5 \times \text{ULN}$ and $\leq 3.0 \times \text{ULN}$ )	
 
Hold study drug/study regimen dose until Grade 2 resolution to Grade <math>\leq 1</math>.
 
If toxicity worsens, then treat as Grade 3 or Grade 4.
 
If toxicity improves to Grade <math>\leq 1</math> or baseline, resume study drug/study regimen after completion of steroid taper.
 
	For Grade 2: 
 
Regular and frequent checking of LFTs (e.g., every 1 to 2 days) until elevations of these are improving or resolved.
 
If no resolution to Grade <math>\leq 1</math> in 1 to 2 days, consider, as necessary, discussing with study physician.
 
If event is persistent (<math>>3</math> to 5 days) or worsens, promptly start prednisone 1 to 2 mg/kg/day PO or IV equivalent.
 
If still no improvement within 3 to 5 days despite 1 to 2 mg/kg/day of prednisone PO or IV equivalent, consider additional work up and start prompt treatment with IV methylprednisolone 2 to 4 mg/kg/day.
 
If still no improvement within 3 to 5 days despite 2 to 4 mg/kg/day of IV methylprednisolone, promptly start immunosuppressives (i.e., mycophenolate mofetil).a Discuss with study physician if mycophenolate mofetil is not
 

available. **Infliximab should NOT be used.**

- Once the patient is improving, gradually taper steroids over  $\geq 28$  days and consider prophylactic antibiotics, antifungals, and anti-PJP treatment (refer to current NCCN guidelines for treatment of cancer-related infections [Category 2B recommendation]).a

Grade 3 or 4	For Grade 3:	For Grade 3 or 4:

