#### **9.1.3.3 Hepatic function abnormalities (hepatotoxicity)**

Immune-mediated hepatitis/hepatic toxicity is the inflammation of the liver. Hepatic AEs induced by PD-1/PD-L1 inhibitors commonly present as asymptomatic increase of AST and ALT, rarely total bilirubin. A proportion of patients may be presenting with fatigue, fever and radiologic appearances including hepatomegaly, periportal lymphadenopathy and periportal oedema (Zhang et al 2016).

As a grouped term, selected hepatic events including laboratory abnormalities were reported at

a frequency of 15.1% (248 patients) across 1645 patients who have received durvalumab monotherapy 10 mg/kg Q2W. Hepatitis events (autoimmune hepatitis, hepatitis toxic, hepatocellular injury, hepatotoxicity and hepatitis acute) were reported at a frequency rate of Uncommon (14 patients; 0.9%). For 9 of the 14 patients, the events of hepatitis were CTC Grade 3 in severity. There were no Grade 4 events. One patient experienced a CTC Grade 5 event of autoimmune hepatitis. Other AESIs such as hepatic failure (5 patients), jaundice (4 patients) and laboratory abnormality AESIs have been observed, two of which resulted in a fatal outcome (CTC Grade 5 hepatic failure and hyperbilirubinaemia). With the durvalumab + tremelimumab combination patients, there were two reports of hepatitis, 1 CTC Grade 1 hepatitis (1 of 560 patients; 0.2%) and 1 CTC Grade 3 autoimmune hepatitis (0.2%) both of

which were considered treatment-related by the reporting investigator. Additionally, there was 1 report of non treatment-related Grade 2 hepatic failure.

Monitoring liver function tests while receiving study medication is important as hepatitis often manifests as asymptomatic elevated levels of hepatic transaminases (ALT, AST, bilirubin; Kim et al 2013). Prompt treatment with steroids is important as per current established toxicity management guidelines.

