## **Pancreatitis**

Pancreatitis is an inflammatory condition of the pancreas that typically manifests initially as asymptomatic elevations of amylase and lipase in patients treated with immune checkpoint inhibitors. Clinical presentation frequently includes low-grade abdominal pain with accompanying fever and malaise (Weber et al 2012, Di Giacomo et al 2010). Biopsies showed diffuse T-cell infiltrate consistent with immune-mediated pancreatitis (Weber et al 2012).

Across the 1645 patients in the monotherapy program, events of pancreatitis were Uncommon to rare. Two patients (0.1%) experienced pancreatitis (CTC Grade 3 and Grade 4 in severity) and 1 patient (<0.1%) with CTC Grade 3 acute pancreatitis. Elevations in amylase and lipase were reported at a frequency rate of Common (0.4% and 0.4%, respectively). In ongoing sponsored studies with durvalumab + tremelimumab therapy in 560 patients, events of pancreatitis were Uncommon; pancreatitis was reported in 4 patients (0.7%) with 3 of these CTC Grade 3 in severity and acute pancreatitis in 1 patient (0.2%). Elevations in amylase and lipase were reported at a frequency of Common (6.1% and 7.0%, respectively). Patients should be monitored for signs and symptoms of pancreatitis including Grade 3 or 4 elevations in lipase and/or amylase.

Prompt treatment of this condition as per current established toxicity management guidelines is important.

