#### **9.3.4.2 Hepatic function abnormality**

Hepatic function abnormality (as defined in Section 10.1.3.3) in a study subject, with or without associated clinical manifestations, is required to be reported as "hepatic function abnormal" ***within 24 hours of knowledge of the event*** to the sponsor and AstraZeneca/MedImmune Patient Safety using the designated Safety e-mailbox (see Section 10.3.2 for contact information), unless a definitive underlying diagnosis for the abnormality (e.g., cholelithiasis or bile duct obstruction) that is unrelated to investigational product has been confirmed.

- If the definitive underlying diagnosis for the abnormality has been established and is unrelated to investigational product, the decision to continue dosing of the study subject will be based on the clinical judgment of the investigator.
- If no definitive underlying diagnosis for the abnormality is established, dosing of the study subject must be interrupted immediately. Follow-up investigations and inquiries must be initiated by the investigational site without delay.

Clinical Study Protocol

Drug Substance Tremelimumab

Study Number **ESR-14-10744**

Edition Number 8

Date 17 April 2019

Each reported event of hepatic function abnormality will be followed by the investigator and evaluated by the sponsor and AstraZeneca/MedImmune.

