## APPENDIX B

### Schedule of study procedures: follow-up for subjects who have completed MEDI4736 or MEDI4736 plus Tremelimumab but did not have resection.

Evaluation	Time Since Last Dose of MEDI4736							
	Day ( $\pm 3$ )	Months ( $\pm 1$ week)						12 Months and Every 6 Months ( $\pm 2$ weeks)
	30	2	3	4	6	8	10	
Physical examination a	X							
Vital signs (temperature, respiratory rate, blood pressure, pulse)	X							
Weight	X							
Urine hCG or serum $\beta$ hCG	X							
AE/SAE assessment	X	X	X					
Concomitant medications	X	X	X					
Palliative radiotherapy	As clinically indicated							
<<World Health Organization>> <<ECOG>> performance status	X	X	X		X (and month 9)			X
Subsequent anti-cancer therapy	X	X	X	X	X	X	X	
Survival status: phone contact with subjects who refuse to return for evaluations and agree to be contacted		X	X	X	X	X	X	X (every 2 months)
Hematology	X	X	X					X
Serum chemistry	X	X	X					
Thyroid function tests (TSH, and fT3 and fT4) b	X							

a Full physical exam

b Free T3 and free T4 will only be measured if TSH is abnormal. They should also be measured if there is clinical suspicion of an adverse event related to the endocrine system.

c For patient questionnaires different approaches based on indication and study design

Clinical Study Protocol

Drug Substance Tremelimumab

Study Number **ESR-14-10744**

Edition Number 8

Date 17 April 2019

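### For dosed patients who undergo resection, no chemistry, hematology or thyroid test is specified after the pre-surgery clinic visit, so 48 to about 83 of the 90 safety days have no protocol-specified bloods

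*Combined protocol and SAP*

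**What the plan says.** In the Schedule of study assessments, the chemistry row ("Serum Chemistry (Complete clin chem. panel including Liver Enzymes, Amylase, Lipase") and the thyroid and hematology rows are marked at screening, at baseline and at the clinic visit before surgery. Their cells in the post-resection follow-up column are empty. The separate liver enzyme panel row has one mark, also before surgery. The follow-up column is in use for other items: physical examination, ECG, adverse events and concomitant medications.

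Section 7.1.3 brings resected patients back 1, 2 and 4 weeks after discharge and then every 4 months, and names only chest CT. It sends unresected dosed patients elsewhere: "Assessments for subjects who have completed MEDI4736 or MEDI4736 + tremelimumab but did not have resection are provided in APPENDIX B". The heading of Appendix B carries the same limit: "follow-up for subjects who have completed MEDI4736 or MEDI4736 plus Tremelimumab but did not have resection". The List of Appendices, section 4.3 and section 7.2.2 refer to Appendix B without that limit.

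The Synopsis (Safety Assessments), section 7 and section 9.3.1 set safety follow-up of 90 days after the dose. Section 7.1 leaves room for unscheduled tests: "Clinical evaluations and laboratory studies may be repeated more frequently if clinically indicated".

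**The concern.** Resection is the intended route for every patient (section 5.3), yet that route has less specified laboratory follow-up than the exception to it. The protocol gives no reason for the difference.

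The toxicities at issue are ones the protocol itself describes as potentially silent. On the liver, section 9.1.3.3 says: "Monitoring liver function tests while receiving study medication is important as hepatitis often manifests as asymptomatic elevated levels of hepatic transaminases". On the pancreas, the text following section 9.1.3.7 says: "Patients should be monitored for signs and symptoms of pancreatitis including Grade 3 or 4 elevations in lipase and/or amylase". Section 9.3.4.2 adds a reporting duty that does not depend on symptoms: "Hepatic function abnormality (as defined in Section 10.1.3.3) in a study subject, with or without associated clinical manifestations, is required to be reported" (the section it cites is now numbered 9.1.3.3). The toxicity guidelines make a Grade 2 transaminase rise a trigger for action: "Regular and frequent checking of LFTs (e.g., every 1 to 2 days) until elevations of these are improving or resolved", with steroids if the rise persists. Each of these steps depends on someone having drawn the blood. An allowance for tests when clinically indicated does not help with a rise that gives no clinical indication.

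What is at stake is detection of immune-mediated hepatic, higher-grade pancreatic and thyroid toxicity in patients recovering from major thoracic surgery. Modest asymptomatic amylase or lipase rises alone would not change management, because the guidelines say they need no steroids.

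**Working it through.** The plan gives no figure for this point, so there is none to reproduce. The check compares the two schedules and counts days from infusion.

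**Inputs**
- Surgery: 1 to 6 weeks after infusion, so day 7 to day 42 (Schedule; section 3.1).
- Clinic visit: printed in weeks 1-6 and held before surgery, so no later than day 42 (Schedule).
- Safety window: 90 days after the dose (Synopsis; sections 7 and 9.3.1).
- Hospital stay: about 8-14 days (section 7.1.3).
- Dosed patients: 8 + 8 = 16 (section 5.3), less any not resected.

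**Step 1: the two schedules side by side, after one dose**

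| Test | Resected (Schedule, 7.1.3) | Not resected (Appendix B) |
|---|---|---|
| Chemistry | none after the pre-surgery clinic visit | day 30, month 2, month 3 |
| Hematology | none after the pre-surgery clinic visit | day 30, month 2, month 3, then month 12 and every 6 months |
| Thyroid | none after the pre-surgery clinic visit | day 30 only |

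If surgery is late, the clinic-visit bloods can fall near or after day 30 and so stand in for Appendix B's first draw. The month 2 and month 3 chemistry and hematology draws have no counterpart in any resected patient. The thyroid contrast is weaker, because Appendix B itself stops at day 30.

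**Step 2: days without specified bloods**

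Gap = 90 − day of last specified bloods.
- Latest case: 90 − 42 = 48 days.
- Earliest case: 90 − 7 = 83 days.

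**Step 3: leaving out the hospital stay, when routine tests are likely**
- Earliest discharge: 7 + 8 = day 15, leaving 90 − 15 = 75 days.
- Latest discharge: 42 + 14 = day 56, leaving 90 − 56 = 34 days.

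**Step 4: is there a planned visit that could carry the bloods?**

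The visit 4 weeks after discharge falls at 15 + 28 = day 43 to 56 + 28 = day 84, before the Schedule's 7-day visit window is applied. That is inside the 90 days and after the last specified bloods.

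**Step 5: what presupposed routine bloods would cover**

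Section 9.3.2 lists events common after resection, in hospital or later in clinic. The laboratory ones are anemia, sodium, potassium and magnesium disturbances, raised creatinine, leukocytosis and acidosis. Liver enzymes, amylase, lipase and TSH are not in the list.

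**The case against.** The strongest reply is that these patients will have bloods anyway. Section 9.3.2 assumes laboratory abnormalities will be seen in hospital and in the post-operative clinic. A reader might infer from the empty follow-up cells that nobody tests these patients after surgery; the documents do not support that. What stands is narrower: the tests are unspecified, and the analytes for silent hepatic, pancreatic and thyroid toxicity are not among those section 9.3.2 implies.

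A reader might also infer that the plan breaks its own monitoring rules. It does not. The statement in section 9.1.3.3 concerns the time while study medication is being received, and here that is one dose. The 24-hour rule in section 9.3.4.2 runs from knowledge of the event, and the guideline on repeat liver tests applies once a rise is known. None of these orders a post-discharge draw. They show why one would be useful.

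Appendix B might be meant for everyone, since three places cite it without limit. Section 7.1.3 and its own heading point the other way, so this is an ambiguity to settle. Unresected patients also lack the admission and early surgical visits, so a separate calendar for them is reasonable. Appendix B keeps unfilled template text as well, which makes it weaker evidence of a deliberate standard.

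Some marks in the extracted table sit a column away from their headers, and the hematology mark could belong to an earlier visit. That would lengthen the gap. No reading puts a blood test in the follow-up column.

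Finally, days are not risk. Section 9.1.3.3 reports hepatitis in 14 of 1645 monotherapy and 2 of 560 combination patients. For 8 patients per arm that is 8 × 14/1645 + 8 × 2/560 = 0.07 + 0.03, or about 0.1 expected cases. Broader laboratory signals are commoner: grouped hepatic events in 15.1% on monotherapy, and lipase rises in 7.0% on the combination. All these rates come from programs that used repeat dosing and do not transfer directly to a single dose. The expected yield is small, which bears on priority but not on whether the gap exists.

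**Conclusion.** The point holds as a gap in the specified safety schedule. On the main pathway, 48 to about 83 of the 90 safety days have no protocol-specified chemistry, hematology or thyroid test; 34 to 75 of those days fall after discharge. This rests on the printed 1-6 week surgery window, the stated 8-14 day stay, and reading Appendix B as limited to unresected patients, as section 7.1.3 and its heading say.

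It does not show that safety follow-up lapses: adverse events are recorded for 90 days and reviewed at all follow-up visits. It has no bearing on the primary endpoint, which uses tumor tissue taken at biopsy and resection. It is a cheap improvement worth making, not a flaw that undermines the trial.

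**What to change.** For all dosed patients, mark chemistry (with liver enzymes, amylase and lipase), hematology and TSH in the follow-up column at one post-discharge visit already planned, preferably the visit 4 weeks after discharge. State the interval as running from discharge: the Schedule's visit header can also be read as cumulative intervals (1 + 2 + 4 = 7 weeks), which would put that visit at 15 + 49 = day 64 to 56 + 49 = day 105, in some cases past day 90. Add one sentence saying whether Appendix B applies to resected patients, and align the List of Appendices, section 4.3 and section 7.2.2 with it.

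The cost is a schedule amendment and one routine blood draw, at an existing visit, for about 16 patients.
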